7.4 Criteria for Early Termination of a Subject's Trial Participation

Under some circumstances, a subject's trial participation may be terminated early. This means that no further trial procedures (including data collection) will be performed on that subject beyond the specific date of early termination of trial participation. The primary reason for early termination of the subject's trial participation should be documented using the following categories:

1. **Adverse Event:** The subject has experienced an AE (irrespective of being related/unrelated to the trial vaccine or trial-related procedures) that requires early termination because continued participation imposes an unacceptable risk to the subject's health and/or the subject's LAR is unwilling to allow the child to continue participation because of the AE. If the subject's LAR is unwilling to allow the child to continue because of the AE, the primary reason for early termination of trial participation in this case will be withdrawal due to AE and not withdrawal of consent, see below.
2. **Lost to follow-up:** The subject did not return to the clinic and at least three attempts to contact the subject's LAR were unsuccessful.
3. **Withdrawal of consent:** The subject's LAR wishes to withdraw from the trial. The primary reason for early termination will be withdrawal of consent if the subject's LAR withdraws the child from participation due to a non-medical reason (i.e., reason other than AE). While the subject's LAR has no obligation to provide a reason for withdrawing consent, attempts should be made to determine the underlying reason for the withdrawal and, where possible, the primary underlying reason should be documented.
4. **Premature trial termination** by the sponsor, a regulatory agency, the IRB, or any other authority.

If the clinical trial is prematurely terminated by the sponsor, the investigator is to promptly inform the trial subject's LAR and local IRB and should assure appropriate follow up for the subjects. The primary reason for early termination in this case will be trial termination.

5. Subject's **death** during trial participation.
6. **Other** reason for early termination that is not captured by the above prespecified categories.

For screen failure subjects, refer to Section 9.1.9.

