8.8 Unblinding Procedure

The trial blind shall not be broken by the investigator unless information concerning HIL-214 is necessary for the medical treatment of a subject. In the event of a medical emergency, if possible, the medical monitor should be contacted before the trial blind is broken to discuss the need for unblinding. For unblinding a subject, the trial vaccine assignment will be obtained by the investigator, by accessing the IRT.

The sponsor's pharmacovigilance department must be notified as soon as possible if the trial blind is broken by the investigator and the completed SAE form, if applicable, must be sent within 24 hours. The date, time, and reason the trial blind is broken must be recorded in the source document and the same information (except the time) must be recorded on the eCRF.

If any subject is unblinded, the subject must be withdrawn from the trial and their data no longer evaluated. Subjects should continue to be monitored for safety follow-up.

8.9 Accountability and Destruction of Sponsor-supplied Trial Vaccine, and Other Clinical Trial Materials

The investigator or designee must ensure that the sponsor-supplied investigational vaccine and placebo are used in accordance with the approved protocol and are administered only to subjects enrolled in the trial. To document appropriate use of sponsor-supplied trial vaccine, the investigator must maintain records of all sponsor-supplied trial vaccine delivery to the site, site inventory, administration and use by each subject, and return to the sponsor or designee.

Upon receipt of sponsor-supplied trial vaccine, the investigator or designee must verify the contents of the shipments against the packing list. The verifier should ensure that the quantity is correct, the trial vaccine is received within the labeled storage conditions (i.e., no cold chain break has occurred during transit), and is in good condition. If quantity and conditions are acceptable, investigator or designee will acknowledge receipt of the shipment by recording in IRT.

If there are any discrepancies between the packing list versus the actual product received, the sponsor or designee must be contacted to resolve the issue. The packing list should be filed in the pharmacy investigator site file.

The investigator must maintain 100% accountability for all sponsor-supplied investigational vaccine and placebo doses, and other clinical trial materials (CTM; including ancillary materials,

CONFIDENTIAL

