5.2 Randomisation and Blinding

Up to 400 subjects (infants aged 2 months [+14 days]) will be enrolled and randomized (1:1) to two arms by interactive response technology (IRT):

- Arm 1 (N=200): HIL-214 (1 dose at 4 months of age and 1 dose at 6 months of age) and routine childhood vaccines according to schedule.
- Arm 2 (N=200): Placebo (1 dose at 4 months of age and 1 dose at 6 months of age) and routine childhood vaccines according to schedule.

The investigator or investigator's designee will access the IRT on Visit 1 to obtain the subject number.

The investigator or investigator's designee will utilize the IRT to randomize all subjects into either the HIL-214 or placebo arms at Visit 2. During this contact, the investigator or designee will provide the necessary subject identifying information. Randomization will be stratified by country.

Randomization information will be stored in a secured area, accessible only by authorized personnel.

The subjects, data collectors (e.g., investigator) and data evaluators are blinded to the material administered.

Trial vaccine administration must be done by designated unblinded site staff, in which the trial vaccine is selected using the subject's number. The designated unblinded site staff must not be involved with data collection of any sort including safety evaluation of the subject after administration of the trial vaccine.

The trial blind shall not be broken by the investigator unless information concerning HIL-214 is necessary for the medical treatment of a subject. In the event of a medical emergency, if possible, the medical monitor should be contacted before the trial blind is broken to discuss the need for unblinding. For unblinding a subject, the trial vaccine assignment will be obtained by the investigator, by accessing the IRT.

If any subject is unblinded, the subject must be withdrawn from the trial and their data no longer evaluated.

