7.1 Analysis Sets

For the purposes of analysis, the subject analysis sets are defined in **Table 3**.

Table 3: Subject Analysis Sets

Subject Analysis Set	Description
Enrolled analysis set	
• All subjects who signed the informed consent
Randomized analysis set	
• All subjects in the enrolled analysis set that were randomized
Immunogenicity evaluable analysis set	
• All subjects in the randomized analysis set that receive all doses of all study vaccines (routine and trial vaccines) within the required time window*
Immunogenicity full analysis set	
• All subjects in the randomized analysis set that receive at least one dose of a trial vaccine within the required time window*
Safety analysis set	
• All subjects in the randomized analysis set who are exposed to the trial vaccine. Subjects will be included in the analyses according to the trial vaccine (HIL-214 or Placebo) they actually received

*This window will be defined at the blinded data review meeting (BDRM)

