8.1 Subject Disposition

Completion/withdrawal from the study and completion/discontinuation from trial vaccine regimen, together with reasons for withdrawal from the study or discontinuation from trial vaccine regimen will be listed and the following will also be tabulated:

- Number and percentage of subjects who completed the study
- Number and percentage of subjects who discontinued trial vaccine regimen early and the principal reason for discontinuation
- Number and percentage of subjects withdrawn from the trial vaccine regimen before randomization and the principal reason for withdrawal
- Number and percentage of subjects withdrawn from the study after randomization and the principal reason for withdrawal
- Number and percentage of subjects withdrawn from the study between Visit 2 and Visit 3 and the principal reason for withdrawal
- Number and percentage of subjects withdrawn from the study between Visit 3 and Visit 4 and the principal reason for withdrawal
- Number and percentage of subjects withdrawn from the study between Visit 4 and Visit 5 and the principal reason for withdrawal

For subjects who fail to meet the eligibility criteria the reasons for failure, including the inclusion/exclusion criteria that were not met will be summarized and listed. This output will use the enrolled analysis set.

The number and percentage of subjects that are randomized to each trial arm will be summarized by country and listed.

The number and percentage of subjects included in each analysis set and the reasons for exclusion will be summarized and listed.

The number and percentage of subjects who attended each scheduled visit (including the early withdrawal visit) will be summarized and listed.

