9.2.1.3 Analysis Methods

For the secondary immunogenicity endpoints data will only be analysed for the patients receiving HIL-214.

A secondary immunogenicity estimand and a supplementary estimand will be created for all of the endpoints outlined in **Section 9.2.1.2**. Analyses will be completed for the two country subgroups only, defined in **Section 7.4**.

For the secondary immunogenicity estimands a complete case analysis will be performed, meaning any subjects with missing data for the parameter of interest will be excluded from the analysis.

For the supplementary immunogenicity estimands for the secondary endpoints the missing data will be accounted for by reweighting the estimates using the method of inverse probability weighting. See **Section 7.5.1** for more details.

For all binary secondary immunogenicity endpoints a standard categorical summary will be presented. SRR is defined in **Section 5.3.2.2**.

For all continuous secondary immunogenicity endpoints a standard continuous summary of the outcome will be presented alongside the GM and GMFR and their confidence intervals. Where country is used as a covariate (see **Section 7.3**) the adjusted GMs will also be presented.

For all secondary immunogenicity parameters a reverse cumulative distribution curve will be produced, with titer/concentration on the x-axis and the percentage of patients below the titer/concentration value on the y-axis. All graphs will present the two vaccine groups which will be overlaid.

Line graphs and boxplots summarizing the GMT for each trial vaccine group for the serotypes GI.1 and GII.4 will also be produced. These outputs will both have the visits of baseline and Visit 4 on the x-axis and the GMT on the y-axis, presenting data on the log scale.

Bar plots for seroresponse, with 95% CIs, will also be created with the results for placebo and HIL-214 stacked next to each other and separate sets of bars for the serotypes GI.1 and GII.4.

10 Safety Analyses

All safety analysis is defined in this section. Along with the following summaries, all safety endpoints will be listed by vaccine group. Where summaries are presented overall, after first dose and after second dose subjects will be summarised under the trial vaccine they receive for that period. If a subject receives HIL-214 for either dose they will be summarised under HIL-214 in the overall summary.

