All safety summaries of continuous variables will present n (non-missing sample size), mean, standard deviation, median, maximum and minimum. All safety endpoint and summaries will use the safety analysis set.

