10.2.5 Serious Adverse Events

10.2.5.1 Summaries

The summaries for SAEs will be:

- The number and percentage of subjects with SAEs during the corresponding collection periods overall
- The number and percentage of subjects with SAEs during the corresponding collection periods by severity
- The number and percentage of subjects with SAEs during the corresponding collection periods by relationship to trial vaccine.
- The number and percentage of subjects with SAEs during the corresponding collection periods by relationship to trial procedure.

All SAEs will be listed.

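### SAP 5.2 excludes unblinded infants' data although the safety set takes every exposed infant, and Table 3's full analysis set requires an in-window dose although its estimand does not

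*SAP*

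**What the plan says.** **Unblinded infants.** SAP 5.2 reads "If any subject is unblinded, the subject must be withdrawn from the trial and their data no longer evaluated". Protocol 8.8 carries the same sentence and then adds "Subjects should continue to be monitored for safety follow-up", which the SAP omits. Protocol 7.4 defines early termination of participation to mean that "no further trial procedures (including data collection) will be performed on that subject beyond the specific date of early termination".

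The analysis sections say something different. The safety analysis set in SAP 7.1, Table 3, is "All subjects in the randomized analysis set who are exposed to the trial vaccine", and SAP 10 adds "All safety endpoint and summaries will use the safety analysis set". Neither the safety data point set (SAP 7.2, Table 4, DPS3) nor Table 9 in SAP 10.1.1 excludes unblinded infants or lists unblinding as an intercurrent event.

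**Immunogenicity full analysis set.** Table 3 admits a randomized infant only if at least one trial vaccine dose fell inside the required window. A footnote leaves that window to the blinded data review meeting. The supplementary estimands apply treatment policy to non-compliance with the trial vaccine schedule (SAP 4.2.1; SAP 9.1.1.1, Table 7). The rationale in SAP 4.2.1 describes their target as infants with one or more doses of HIL-214 or placebo, with no window condition. They are evaluated on DPS2, which starts from the full analysis set.

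**The concern.** In both places, text about who is analysed can remove infants whom another part of the plan says are analysed.

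For safety, two programmers could produce different tables from the same data, one following SAP 5.2 and the other following Table 3. The investigator may break the blind only when the information is needed for an infant's treatment, so losses from investigator code-breaks would not be a random subset. The affected infant may be the one whose event matters most in the summaries.

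For immunogenicity, the supplementary analysis is the plan's check on what happens when schedule deviations are kept in. If infants with no in-window dose are removed first, the analysis does not estimate its stated target.

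**Working it through.** **Part 1: three readings of the exclusion clause**

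Inputs: 200 per arm (SAP 6); safety tables give counts, percentages and event numbers, overall and by country (SAP 10.1.2). The documents give no unblinding rate, so the cases below are illustrations with assumed counts.

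| Reading | What leaves the safety tables | Example in an arm of 200 |
|---|---|---|
| Retroactive | The infant and all the infant's events | Only SAE in the arm: 1/200 = 0.5% becomes 0/199 = 0% |
| Prospective | Events collected after unblinding | That SAE stays at 1/200; a new preferred term after unblinding goes from 1/200 to 0/200 |
| Table 3 prevails | Nothing | 1/200 stays 1/200 |

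Three further points on the size:
- With more events the retroactive effect is less stark. If four infants had an SAE and one was dropped, 4/200 = 2.00% becomes 3/199 = 1.51%.
- An event the dropped infant did not have barely moves: 20/200 = 10.00% becomes 20/199 = 10.05%.
- Country summaries are more sensitive. At the minimum US target of 100 infants (Protocol 4.2), 1:1 allocation stratified by country gives about 50 per arm, and 1/50 = 2.0% becomes 0/49 = 0%.

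The prospective loss requires later data to be collected and then left out. Protocol 8.8 suggests that they are collected. If Protocol 7.4 governs the withdrawal, they are not, and there is nothing to drop.

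**Part 2: infants with no in-window trial dose**

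Let p be the probability that a given dose is out of window, and q the fraction of infants who receive only one dose. Neither is in the documents; I assume p = 5–10% and q = 0–5%.

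If the two doses are independent, the expected loss per 200 is 200 × [(1 − q)p² + qp].
- q = 0, p = 5%: 200 × 0.0025 = 0.5
- q = 0, p = 10%: 200 × 0.01 = 2.0
- q = 2%, p = 5%: 200 × (0.98 × 0.0025 + 0.02 × 0.05) = 0.69
- q = 5%, p = 10%: 200 × (0.95 × 0.01 + 0.05 × 0.10) = 2.90

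The range is therefore about 0.5–3 per 200.

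Dependence would raise this, and whether it arises turns on how the window is set. Visit 1 allows +28 days, and randomization is scheduled 2 months after screening (Protocol 2.2, footnote b). Dose 1 is described at 4 months +7 days (Protocol 4.2). An infant enrolled on the last permitted day and seen 2 months later is 28 − 7 = 21 days past that limit. Under an age-based window such an infant could miss on both doses. Under the interval in Protocol Table 2.1 (Visit 3 timed from Visit 2, ±7 days), dose 2 can still be in window, and the infant stays.

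**Can the weighting restore them?** No. In SAP 7.5.1 the weights are 1/P(complete case | trial vaccine option), and the denominators N₁ and N₂ count subjects in the analysis set. Infants outside the set enter neither.

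**The case against.** **On part 1.** The clause sits under randomization and blinding. The sets in SAP 7.1 are the ones defined for analysis, and they contain no exclusion for unblinding. It is reasonable to expect Table 3 to prevail. A prospective reading is also natural, and it leaves the infant and the triggering event in place. A reader might infer that safety data are lost on any reading. The documents do not support that: nothing is lost if Table 3 governs, or if the clause is prospective and Protocol 7.4 stops later collection.

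A reader might also infer that every excluded infant was selected by medical need. That limit applies to code-breaks by the investigator, whereas the exclusion covers any unblinded subject. HIL-214 and placebo look different (Protocol 8.1.2 and 8.5), so accidental unblinding is possible and falls under the same sentence.

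Nor would a case disappear from the report. SAP 10 says "all safety endpoints will be listed by vaccine group", SAP 10.2.5.1 says "All SAEs will be listed", and SAP 8.1 says "The number and percentage of subjects included in each analysis set and the reasons for exclusion will be summarized and listed". No confidence limits are specified for the safety tables, so the effect there is on counts and percentages. These points stand and limit the size. They do not settle which rule applies.

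**On part 2.** DPS2 keeps all data of infants vaccinated out of window. It can be read consistently with Table 3, as covering an infant with one dose in window and one outside it. I accept that, so the conflict is between Table 3 and the estimand in SAP 4.2.1 and Table 7, not with DPS2. A reader might also take full dependence between doses (200 × p = 10–20 infants per 200) as the expected loss. The documents do not support that, because it needs an age-based window, none has been set, and Visit 3 is timed from Visit 2.

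**Conclusion.** Both inconsistencies are in the current text and should be corrected, but the likely effects are small.

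(1) SAP 5.2 and Protocol 8.8 exclude an unblinded infant's data without a safety exception, while Table 3 and SAP 10 include every exposed infant, and no rule of precedence is given. What is shown is an unresolved conflict that could remove safety data, not a demonstrated loss. In the illustration it changes one infant per arm (1/200 to 0/199). The direction between arms is unknown, and the number of unblinded infants cannot be derived from the documents.

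(2) The full analysis set removes infants with no in-window trial dose from an analysis whose estimand includes them. Under the assumed 5–10% of doses out of window and independent doses, this is about 0.5–3 per 200, and more only if an age-based window puts both doses of late starters out. Infants with one dose in window and one out stay in. Only the supplementary immunogenicity estimands are affected; the primary and secondary estimands use DPS1.

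**What to change.** - **SAP 5.2:** state that the exclusion of unblinded infants does not apply to safety, and that all collected safety data of exposed unblinded infants, before and after unblinding, stay in the safety analysis set. Record this in SAP 13, because it departs from the sentence in Protocol 8.8.
- **Protocol 8.8 and 7.4:** these must be reconciled on whether data collection continues after an unblinded infant is withdrawn. This can be done at the next amendment.
- **SAP 7.1, Table 3:** delete the time-window condition from the immunogenicity full analysis set, so that it reads as randomized infants with at least one dose of trial vaccine.

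The cost is two SAP wording changes and one line in SAP 13, all before unblinding. No new data or analyses are needed; a few more infants may enter the supplementary tables.

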5.3 Derived variables

5.3.1 General

5.3.1.1 Baseline

Unless otherwise stated, baseline is defined as the last non-missing pre-trial vaccine assessment prior to the first trial vaccine.

5.3.1.2 Relative Day

The relative day from first routine vaccine of an assessment will be calculated as:

- For measurement performed on or after the date of first dose of routine vaccine:
Date of assessment – date of first routine vaccine + 1
- For measurements performed before the date of first dose of routine vaccine:
Date of assessment – date of first routine vaccine

The relative day from first dose of trial vaccine of an assessment will be calculated as:

- For measurement performed on or after the date of first dose of trial vaccine:
Date of assessment – date of first trial vaccine + 1
- For measurements performed before the date of first dose of trial vaccine:
Date of assessment – date of first trial vaccine

5.3.1.3 Demographic and Background Data

Age at screening will be calculated in days. Age at screening will be calculated as follows:

$$\text{Age at Screening (days)} = \text{Screening date (Visit 1)} - \text{Date of Birth} + 1.$$

Weight may be recorded in kilograms or pounds. Weight in pounds will be converted to weight in kilograms as follows:

$$\text{Weight (kg)} = \text{Weight (lb)} * 0.4536.$$

Weight will be presented to 1 dp in the listings.

Length may be recorded in centimetres or inches. Length in inches will be converted to length in centimetres as follows:

$$\text{Length (cm)} = \text{Length (inches)} * 2.54.$$

Length will be presented to 1 dp in the listings.

Head Circumference may be recorded in centimetres or inches. Head circumference in inches will be converted to head circumference in centimetres as follows:

$$\text{Head circumference (cm)} = \text{Head circumference (inches)} * 2.54.$$

Head circumference will be presented to 1 dp in the listings.

Temperature may be recorded in Degrees Celsius or Fahrenheit. Temperature in Fahrenheit will be converted to temperature in Degrees Celsius as follows:

$$\text{Temperature } ({}^\circ\text{C}) = (\text{Temperature } ({}^\circ\text{F}) - 32) * 0.5556.$$

Temperature will be presented to 1 dp in the listings.

